### 14.3.9 Electrocardiogram (ECG)

#### 14.3.9.1 Electrocardiogram - Overall interpretation

Population: Safety Population

Characteristics	Treatment Group
. Visit 1 (Screening), Visit 6 (Day 14, EOT), N (Missing)	XXX (XXX)
Normal	XXX (XX.X%)
NCS	XXX (XX.X%)
CS (Medical History)	XXX (XX.X%)
CS (Adverse Event)	XXX (XX.X%)
Visit 1 (Screening) to Visit 6 (Day 14, EOT)	
N (Missing)	XXX (XXX)
Relieved	XXX (XX.X%)
Unchanged	XXX (XX.X%)
Worsened (Medical History)	XXX (XX.X%)
Worsened (Adverse Event)	XXX (XX.X%)

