3. STUDY OBJECTIVES AND ENDPOINTS

Primary Objective	Primary Endpoint
To assess safety and tolerability of CX-4945 administered orally BID to patients with moderate COVID-19	
Adverse events occurring from randomization (Day 1) to Day 60 (including vital signs, physical findings, clinical laboratory, and ECG results) as characterized by type, frequency, severity [(as graded by Toxicity Grading Scale for Healthy Adult and Adolescent Volunteers Enrolled in Preventive Vaccine Clinical Trials (https://www.fda.gov/media/73679/download)], timing, seriousness, and relationship to study therapy.
Secondary Objectives	Secondary Endpoints
To compare time to normalization of COVID-19-related clinical signs in CX-4945 treatment arm versus the control arm.	
Number of days from Randomization (Day1) to the day when the following clinical signs are back to normal as evaluated at every visit during the treatment period (Day 1, Day 4, Day 8, Day 11 and Day 14) and at Follow-up visits on Day 28 and Day 45 :
 
Fever is $\leq 36.6^{\circ}\text{C}$ from axillary site, or $< 37.2^{\circ}\text{C}$ from oral site or $< 37.8^{\circ}\text{C}$ from rectal or tympanic site)Respiratory rate is < 20 bpm while breathing room air at sea level$\text{SPO} \geq 96\%$ in room air without shortness of breath or dyspneaHeart rate < 90 beats per minute 
Note: If some signs listed above were caused by other conditions documented in the medical history and started before COVID-19, the patient can be considered as recovered, when these signs return to the previous (pre-COVID-19) values.

To compare duration of COVID-19-Related clinical symptoms in CX-4945 treatment arm versus the control arm.	Number of days from Randomization (Day1) to the day when: 
No key COVID-19-related symptoms scored higher than 1 as documented using a Patient Reported Outcome (PRO) instrument (a Patient Diary for Assessment of Common COVID-19-Related Symptoms – see Appendix 3),

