8.2.1.5. ECG

An ECG will be done at Screening and at Day 14/EOT. It is preferable that the machine used has a capacity to calculate the standard intervals automatically, including QT and QTc interval. At each time point (see the Schedule of Activities), if the significant abnormalities (>Grade 2) in ECG intervals are revealed, then the ECGs should be re-evaluated by a qualified person at the site for confirmation as soon as the finding is made, including verification that the machine reading is accurate.

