8.2.1.6. Other Assessments

To adequately monitor for the risk of 5-HT3 antagonist pre-medication which may predispose patients to arrhythmias, 24-hour telemetry monitoring for patients with electrolyte abnormalities may be performed, if clinically indicated.

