9.2. DESCRIPTION OF STUDY OUTCOMES (ENDPOINTS)

For description of study outcomes see the Objectives and Endpoints in Section 1.1 and Section 3.

9.2.1. Safety Measures:

- Incidence and severity of AEs
- Incidence of SAEs
- Incidence of AEs and SAEs leading to discontinuation of study medication.
- Changes in blood chemistry (including electrolyte abnormalities), hematology and coagulation parameter results
- Changes in vital signs including temperature, pulse, respiratory rate, systolic and diastolic blood pressure
- Changes in physical examination results
- Changes in ECG results

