9.8.4.3. Safety Summaries

Adverse Events

AEs will be coded using the most recent version of Medical Dictionary for Regulatory Activities (MedDRA). Treatment Emergent AE's (TEAE) are defined as events with an onset on or after the first treatment. TEAEs will be summarized by treatment group, system organ class, and preferred term. The following TEAE summaries will be provided:

- Overall (i.e., regardless of severity or relationship to treatment);
- By intensity (mild, moderate, severe, life threatening or death);
- By causality (definitely, probably, possibly, remotely or unrelated);
- By impact on study treatment (dose increased, dose not changed, dose rate reduced, dose reduced, drug interrupted, drug withdrawn, not applicable, or unknown).

In addition, separate summaries of SAEs, and AEs resulting in discontinuation of study treatment will be presented.

Clinical Laboratory Data

All laboratory values will be listed. Laboratory measurements will also be summarized and presented by treatment group and time point.

ECG

All ECG values will be listed. ECG measurements will also be summarized and presented by treatment group and time point.

Vital Signs

All vital sign findings will be listed and/or summarized.

Physical Examination

All physical examination findings will be listed and/or summarized.

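### The protocol promises ECG measurements summarized by arm and time point; the SAP tabulates only a four-category overall interpretation and does not declare the change

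*SAP*

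**What the plan says.** **Protocol.** Section 9.8.4.3 makes two commitments on ECG: "All ECG values will be listed", and "ECG measurements will also be summarized and presented by treatment group and time point". Section 9.2.1 names "Changes in ECG results" as a safety measure. The primary endpoint in section 3 is adverse events, "including vital signs, physical findings, clinical laboratory, and ECG results". On timing, section 8.2.1.5 states: "An ECG will be done at Screening and at Day 14/EOT". It prefers, but does not require, a machine with the "capacity to calculate the standard intervals automatically, including QT and QTc interval", and it asks the site to re-evaluate interval abnormalities above Grade 2. Section 8.2.1.6 refers to 5-HT3 antagonist premedication, "which may predispose patients to arrhythmias". Section 6.1.3 ties antiemetic prophylaxis to each CX-4945 dose.

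**SAP.** Section 14.3.9 contains one table, 14.3.9.1 "Electrocardiogram - Overall interpretation". By arm and at both time points it counts four categories: normal, NCS, clinically significant from medical history, and clinically significant as an adverse event. It then gives the Screening to Day 14 transition as relieved, unchanged or worsened (two kinds). Item (7) of the Instructions and Abbreviations puts Normal to NCS, and the reverse, under Unchanged. Section 1 says that the SAP follows the protocol apart from the exceptions it sets out. Sections 1.1 to 1.6 cover visit adjustment, the per-protocol population, compliance, analysis methods, missing values and pharmacokinetics. None mentions ECG.

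**The concern.** An overall interpretation is a judgement about a tracing, and the intervals are the measurements. The protocol promises a summary of the measurements and the SAP shells deliver only the judgement. Because section 1 is where departures are declared, a reader of the SAP would not know that anything had been dropped.

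Safety is the trial's primary objective, and the protocol itself raises an arrhythmia risk from premedication that goes with CX-4945 dosing. The trial is also open-label (Protocol 9.5), so whether an abnormality is called clinically significant is decided by someone who knows the arm. Recorded intervals depend less on that judgement. What is at stake is whether the report shows, by arm, how far the intervals moved between Screening and Day 14/EOT.

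**Working it through.** The documents give no figure on this point, and Protocol 9.3 states that the sample size has no power basis, so there is nothing to reproduce. The check is a comparison of texts, followed by an illustration of what the missing table could show.

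**Step 1: promise against delivery.**

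| Data type | Protocol 9.8.4.3 | SAP shells |
|---|---|---|
| Laboratory | listed, and measurements summarized by arm and time point | mean, SD, median, range, change from baseline, CIs |
| Vital signs | listed and/or summarized | the same statistics, with ANCOVA or Wilcoxon on change |
| ECG | listed, and measurements summarized by arm and time point | interpretation categories and transition only |

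The ECG commitment is worded like the laboratory one, and the SAP carries out the laboratory one numerically. Vital signs have a looser commitment and still receive full numeric tables. ECG intervals have no numeric row.

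**Step 2: where a prolongation judged NCS would appear.** Take a patient who is Normal at Screening and has a longer interval at Day 14, read as NCS.

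- Transition rows of 14.3.9.1: counted as Unchanged, not Worsened.
- Adverse event tables: absent, because Protocol 8.3.1 says that abnormal findings without clinical significance are not recorded as adverse events.
- By-visit category counts: one more NCS at Day 14. These are net counts, so one patient moving from Normal to NCS and another moving back leave the total the same. They give neither the interval nor its size.
- Listing: present under Protocol 9.8.4.3, if the interval was recorded.

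**Step 3: precision of an interval summary.** Inputs: about 20 patients randomized 1:1 (Protocol 9.3), so n = 10 per arm at best. The SD of QTc change is not in the documents; 10 to 25 ms is an assumption.

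Half-width of the 95% CI for the between-arm difference in mean change = t(0.975, 18) × SD × √(2/10) = 2.101 × SD × 0.447 = 0.940 × SD.

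| Assumed SD of change (ms) | 95% CI half-width (ms) | Power for a 10 ms shift | Power for a 20 ms shift |
|---|---|---|---|
| 10 | 9.4 | 61% | 99% |
| 15 | 14.1 | 32% | 85% |
| 20 | 18.8 | 20% | 61% |
| 25 | 23.5 | 14% | 43% |

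Power is two-sided at 5% by normal approximation. The 10 and 20 ms shifts are illustrations, not document values.

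**The case against.** The strongest reply is that little is lost. The protocol promises a listing of every ECG value, which for about 20 patients with two scheduled ECGs each is about 40 tracings and can be read by eye. Interval abnormalities above Grade 2 are re-evaluated at the site, and clinically significant findings are counted in 14.3.9.1 and reach the adverse event tables. The table is also more than a normal/abnormal split, and it covers change in ECG results categorically. ECG enters the primary endpoint through adverse events, and no endpoint names mean QTc. Since the SAP defers to the protocol where it declares no exception, the commitment arguably still applies by default.

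Most of this stands, and it limits the point. A reader might infer that a QTc shift would go unseen. The documents do not support that: it would be listed but not summarized. A reader might also infer that an interval table would settle whether a moderate shift occurred. Under the assumed SDs, power for a 10 ms shift ranges from 61% down to 14%. Automatic QT and QTc output is only preferred, so n may fall below 10 per arm. Prophylaxis goes with CX-4945 dosing, so an arm difference could not be attributed to the drug rather than the antiemetic. A tally of ECGs above Grade 2 may also look natural, but the grading scale as described in Protocol 8.3.3.1 does not mention ECG intervals and Appendix 2 is only a link, so the documents give no ECG grade to count.

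The reply does not remove the mismatch. A listing is the protocol's other commitment, not a substitute for the summary, and deference by default produces no table when the shells contain none.

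**Conclusion.** The point holds as an undeclared departure from the protocol. ECG measurements were to be summarized by arm and time point, and no SAP table does so. As a result, an arm-level shift in intervals would appear only in listings, and a prolongation judged NCS would appear in no Worsened row and no adverse event table, only in the by-visit NCS counts.

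It is a gap in safety description and invalidates no planned analysis. The gain from closing it is modest: an estimate of size with a half-width of about 9 to 24 ms, which rests on 10 evaluable patients per arm and an assumed SD of change of 10 to 25 ms. Fewer recorded intervals would widen it. The documents do not show whether intervals were captured for every patient.

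**What to change.** Add a descriptive table 14.3.9.2 for the Safety population: recorded PR, QRS, QT and QTc at Screening and Day 14/EOT by arm, with n (missing), mean, SD, median and range, and change from screening with a 95% CI. Heart rate is already summarized in 14.3.8.5. In 14.3.9.1, show Normal-to-NCS transitions as their own row, with a footnote that this departs from the SAP's common transition definition for this table. If intervals were not captured, say so in SAP section 1 and explain why the protocol's summary is not produced.

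The cost is one table and one extra row, using values the protocol already says will be listed. The table should be labelled descriptive, with a note that it cannot separate CX-4945 from its antiemetic premedication.
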